## Observational PASS

Title	Iodinated contrast agents and risk of hypothyroidism in young children in the United States
Protocol version identifier	1.0
Date of last version of protocol	11 Oct 2016
EU PAS register number	Not registered
IMPACT number	19185
Phase	N/A
Active substance	N/A
Medicinal product	Iodinated contrast agents, e.g. iopromide
Product reference	NA
Procedure number	NA
Marketing authorization holder(s)	N/A
Joint Pass	No
Research question and objectives	This study will estimate the incidence of hypothyroidism in a pediatric population of children under age 4, based on data from the US-based Kaiser Permanente Northern California database, who were exposed to iodinated contrast agent through having a diagnostic procedure.
Country(-ies) of study	United States
Author	[name] Director: Boston Collaborative Drug Surveillance Program PPD [REDACTED] PPD [REDACTED] USA

## 2. List of abbreviations

BCDSP	Boston Collaborative Drug Surveillance Program
BU	Boston University
CI	Confidence Interval
CPT	Current Procedural Terminology
DMP	Data Management Plan
DRG	Diagnosis-Related Group
FDA	Food and Drug Administration
FFS	Fee-For-Service
GCP	Good Clinical Practice
HCPCS	Healthcare common procedure coding system
HMO	Health Maintenance Organization
HR	Hazard Ratio
ICD	International Classification of Diseases
IRB	Institutional Review Board
IT	Information Technology
KPNC	Kaiser Permanente Northern California
N/A	Not Applicable
NDC	National Drug Code
SAP	Statistical Analysis Plan
STROBE	Strengthening the Reporting of Observational Studies in Epidemiology
US	United States
WHO DD	World Health Organization Drug Dictionary

### 4. Abstract

**Title:** Study of Iodinated contrast agents and risk of hypothyroidism in young children in the United States

**Rationale and background:** While it is generally known and acknowledged that exposure to iodine contrast can interfere with thyroid function, little is known about the incidence of iodine-induced hypothyroidism in young children (under age 4).

**Research question and objectives:** The goal of this study is to estimate the incidence rate of detected hypothyroidism in a US-based general population of patients less than 4 years of age during years 2008 - 2015, who were exposed to an iodinated contrast agent.

**Study design:** This will be a retrospective cohort study.

**Population:** Patients less than age 4 in the US-based *Kaiser Permanente Northern California* data during years 2008 through 2015

**Variables:** Age, sex, calendar year, diagnostic procedure, comorbidities, treatments

**Data sources:** *Kaiser Permanente Northern California* database

**Study size:** There are millions patients under age 4 in the *Kaiser Permanente Northern California* database. From these data we expect to identify around 2300 pediatric patients who had a diagnostic procedure with an iodinated contrast agent.

**Data analysis:** We will estimate incidence rates of hypothyroidism in the 365 days post exposed procedure. We will also describe these patients according to characteristics, comorbidities, treatments, and diagnostic procedure received, as well as the time-relation between contrast exposure and hypothyroidism

**Milestones:** A preliminary report will be provided by December 2016 and a final report by 31 March, 2017

### 5. Amendments and updates

None

## 6. Milestones

**Table 1 Milestones**

Milestone	Planned date
Finalize study protocol	September, 2016
Obtain PPD approval	September 2016
Start of data collection	October 2016
End of data collection	November 2016
Preliminary report	22 December 2016
<Registration in the EU PAS register>	tbd
Final report of study results	31 March, 2017

## 7. Rationale and background

It is generally accepted that iodinated contrast agents can cause thyroid dysfunction because of the free iodide in the contrast solution. While a typical dose of 100 ml of contrast agent with an iodine concentration of 300 mg iodine/ml contains 30 g of bound iodine, the same solution also contains unbound or free iodine. Typical values of free iodide present in contrast material are

CCl

. The actual amount of free iodide administered to a patient depends on the total dose, concentration and time between production of contrast agent and use.

Excessive free iodide may inhibit thyroid hormone synthesis, causing hypothyroidism through an acute Wolff-Chaikoff effect. Normal thyroid hormone synthesis typically resumes after the acute Wolff-Chaikoff effect is corrected. Because neonates have immature thyroid tissue, they are especially susceptible to the Wolff-Chaikoff effect. Since it is known that thyroid hormones are essential for the development of newborn and infants, hypothyroidism may pose a serious threat to a child's physical and mental development if left untreated. Hypothyroidism can affect both newborns and older children and can lead to delayed growth, overweight, enlargement of the thyroid gland, among other symptoms. In very young children prolonged hypothyroidism can lead to development delay.

The incidence of hypothyroidism after exposure to iodinated contrast agents is unknown in this patient population. In a literature review by Ahmet et al. nine studies were analyzed examining the effects of iodinated i.v. contrast media on thyroid function of neonates. Overall 8.3% of the term infants and 18.3% of the premature infants developed hypothyroidism after iodinated contrast media exposure; suggesting that preterm infants have an increased risk of hypothyroid compared to term infants. The authors noted that all studies were highly affected by bias. A retrospective database-study in a mainly adult patient population reported that iodinated contrast media exposure was associated with incident hyperthyroidism (odds ratio [OR], 1.98; 95% CI, 1.08-3.60), while no statistically significant association with incident hypothyroidism was observed (OR, 1.58; 95% CI, 0.95-2.62) (Rhee et al, Arch Int Med, 2012). In secondary analyses

an association with incident overt hypothyroidism was described. Due to its design, the study could not report incidence estimates of hypothyroidism following contrast exposure.

In general, hypothyroidism in children can have a wide variety of different etiologies including Hashimoto thyroiditis, some chromosomal disorders (Down Syndrome, Turner Syndrome), late-onset congenital hypothyroidism, as well as central hypothyroidism caused by pathologies in the pituitary gland or hypothalamus (Counts D et al. , 2009). Acquired childhood hypothyroidism, a result of decreased thyroid production caused by a failure in the hypothalamus and pituitary, has multiple causes including irradiation, drug exposures, iodine deficiency, neurosurgery, head trauma, tumors, or thyroid hormone resistance. Drugs such as thionamides, lithium, amiodarone, interferon, and anticonvulsants are known to suppress thyroid function or interfere with thyroid synthesis.

We plan to estimate, in a large health maintenance organization (HMO) in Northern California, the rate of detected hypothyroidism in young children (age less than 4 years) exposed to an iodinated contrast agent.

## **8. Research questions and objectives**

### **8.1 Primary objective**

The goal of this study is to estimate the incidence rate of hypothyroidism, detected in routine clinical practice, in a US-based general population of patients less than 4 years of age during years 2008 - 2015, in the 365 days post exposure to an iodinated contrast agent. .

Hypothyroidism cases will be categorized into “probable iodine-induced hypothyroidism” and “possible alternative etiology” after medical records review.

### **8.2 Secondary objective(s)**

The secondary objective(s) in this study is/are:

- To describe children who have procedures with iodinated contrast agents
- To describe the baseline characteristics of hypothyroidism cases and of the rest of the cohort as well as the time-relation between iodine contrast exposure and diagnosis of hypothyroidism, using descriptive statistics. This will be done for all hypothyroidism cases and separately for the “probable iodine induced” category and the “possible alternative etiology” category. In the “probable iodine induced” category we will further

ascertain the duration of the hypothyroidism episode.

## **9. Research methods**

### **9.1 Study design**

This will be a retrospective cohort study to describe patient characteristics and incidence of hypothyroidism in a pediatric population of children up to 365 days after a diagnostic scan with iodinated contrast agent. The study will be based on secondary data collection only.

### **9.2 Setting**

This study will be conducted using data from the Kaiser Permanente Northern California (KPNC) database, a large US-based HMO database.

#### **9.2.1 Study time frame**

We will identify all patients in the KPNC database who were under age 4 during the years 2008 through 2015.

#### **9.2.2 Selection criteria**

We will identify all patients who were in the KPNC database and who were under age 4 at some time during the years 2008 through 2015.

#### **9.2.3 Study population**

The study population will be all patients who were under the age of 4 at some time during the years 2008 to 2015 in the US- based KPNC database who had a procedure with iodinated contrast agent. A preliminary search of the data identified around 2300 people under age 4 who had a procedure with iodinated contrast, by searching CPT and HCPCS codes. We will also require that all children in the study were members of KPNC for at least 3 months before the iodinated contrast exposure, except where the child is under 3 months of age at time of initial exposure, and 2 weeks after the exposure. From this population we will exclude all children who had a diagnosis of hypothyroid any time prior to the iodine contrast exposure. We will also exclude those with lab values for low thyroid (TSH > 5 mU/L for children) any time before the

exposure, and those with thyroid replacement therapy, Hashimoto thyroiditis, or congenital hypothyroidism any time prior to the exposure.

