## **9.3 Variables**

### **9.3.1 Baseline characteristics**

- Demographics characteristics (age, sex, year of procedure)
- Clinical characteristics (comorbidities, type of radiological examination, bodyweight, height, head-circumference, laboratory values (TSH, T3, T4 anti-thyroid antibodies, if available), and co-medications.

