## **9.4 Data sources**

KPNC is an integrated health care delivery system providing health care to over 3.8 million members with 3,300 physicians, 32 outpatient clinics and 17 hospitals. Analysis of U.S. census data demonstrates that KPNC members are representative of the population living in the served geographic area. KPNC maintains medical information on each patient through a computerized

EHR database called “Health Connect” since 2007. Therefore, we have access to high quality clinical data.

Admitting, Discharge and Transfer (ADT) System. A complete database on all hospitalizations at any KPNC hospital since 1971 is maintained with data that are highly comparable to the UB-92 forms (required of all hospitals in California and most other States), and contains a principal and up to 12 secondary discharge diagnoses and codes for up to seven procedures for each hospitalization. Admitting and discharge diagnoses and procedures are coded according to the International Classification of Disease, 9th revision (ICD-9). The accuracy of principal discharge diagnoses obtained from Kaiser Permanente databases has been verified in other studies.

The Laboratory Utilization and Reporting System (LURS) is a clinical database that captures all laboratory tests and results performed at the Kaiser Permanente of Northern California regional laboratory since 1991. In 1995, LURS incorporated all hospital-based laboratories of Northern California. Providers use this system to order tests, obtain results and share them with patients. Thus, data in LURS are of higher quality than a chart review study could achieve (since chart review involves small rates of reviewer and transcription error). LURS contains patient name, medical record number, test name (each test has a unique code), date, and result. Essentially all thyroid tests ordered are available in the LURS database.

Outpatient Service Clinical Record (OSCR), a computerized database, will be a source to identify outpatient diagnosis of thyroid disorders.

The database contains a unique identifier for all information on all drugs issued to patients, all hospitalizations, captured with ICD-9 coding, outpatient diagnoses and laboratory tests and result. KPNC membership is stable and more than 97% of members have 5 or more years of membership.

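### The thyroid exclusions cover the child's whole life, but only 3 months of prior membership is guaranteed, and none under 3 months of age, so some prevalent disease can be counted as incident

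*Combined protocol and SAP*

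**What the plan says.** Section 9.2.3 sets the thyroid exclusions without a time limit. The study will "exclude all children who had a diagnosis of hypothyroid any time prior to the iodine contrast exposure". Another step is to "exclude those with lab values for low thyroid (TSH > 5 mU/L for children) any time before the" contrast procedure, and children with "thyroid replacement therapy, Hashimoto thyroiditis, or congenital hypothyroidism any time prior to the exposure" are also left out.

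The same section sets the observation that these exclusions rely on. Children must have been "members of KPNC for at least 3 months before the iodinated contrast exposure". A waiver then qualifies this within the same sentence: "except where the child is under 3 months of age at time of initial exposure, and 2 weeks after the exposure". The closing words of that sentence concern membership after exposure. For an infant under 3 months, nothing is required before it.

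No thyroid test at baseline is required. Section 9.3.1 lists "laboratory values (TSH, T3, T4 anti-thyroid antibodies, if available" among the baseline variables.

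Section 9.3.3 adds a second check. The record of every potential case is reviewed for hypothyroidism that predates contrast, and clinical notes are then searched for earlier and congenital thyroid disease. Section 9.8 repeats that complete medical records are used to validate all cases. Detected cases then fall into three classes: probable iodine-induced (no other cause found), possible alternative etiology, or not a case. Rates are reported for all cases together and by category.

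**The concern.** The study's main result is an incidence rate, so each counted case should have been free of the disease at entry. Here the exclusion window is the whole of life, while the guaranteed observation is 3 months or nothing. A child diagnosed or treated outside KPNC before joining can have an empty KPNC thyroid history. Without a required baseline test, an empty history passes as a clean one. The first KPNC code, raised TSH or thyroid prescription after contrast then makes that child a potential case.

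The waiver falls on the age group that the rationale singles out: "Because neonates have immature thyroid tissue, they are especially susceptible to the Wolff-Chaikoff effect". Congenital disease also belongs to this age, predates any exposure by definition, and appears (code 243) in the Annex 3 list of codes for finding hypothyroidism. Section 9.9 does not mention short history as a limitation, and the Annex 2 checklist marks both selection and information bias as not applicable.

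**Working it through.** The plan has no figure of its own to reproduce on this point. The 2300 in sections 9.2.3 and 9.5 is a count from a preliminary search, not the output of a formula.

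**Step 1. Guaranteed history against the exclusion window.** Inputs: 3 months of membership and an unlimited exclusion window (section 9.2.3). Guaranteed share of life = 3 / age in months.

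| Age at exposure | Guaranteed history | Share of life | Possibly unobserved |
|---|---|---|---|
| under 3 months | none | 0 | less than 3 months |
| 6 months | 3 months | 3/6 = 50% | 3 months |
| 12 months | 3 months | 3/12 = 25% | 9 months |
| 24 months | 3 months | 3/24 = 12.5% | 21 months |
| 36 months | 3 months | 3/36 = 8.3% | 33 months |
| just under 48 months | 3 months | 3/48 = 6.25% | about 45 months |

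These are minimums, because longer history is used where it exists. They are shares of time, not probabilities of missing disease.

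**Step 2. Follow one child through the rules.** Take an infant aged 10 weeks who joins on the day of the scan.
- Entry (9.2.3): eligible, with no observable history.
- Outcome (9.3.3): a first code, TSH above 5.0 mU/L or thyroid prescription within 365 days makes a potential case.
- Review (9.3.3): if a KPNC clinician noted earlier outside disease, the review can find it. The documents describe no retrieval of outside records, so without such a note it cannot.
- Classification (9.3.3): with no other cause found, the case becomes probable iodine-induced. None of the three classes covers disease that was already present, or prior status that cannot be observed.

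**Step 3. Effect of one false case.** Assume that all 2300 children are followed for 365 days, giving 2300 person-years. One false case adds 1/2300 × 1000 = 0.43 per 1000 person-years. Less person-time would make the increment larger.

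Illustration with assumed case counts and exact Poisson 95% intervals:

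| True cases | False cases | Rate per 1000 person-years (95% CI) | Change |
|---|---|---|---|
| 10 | 0 | 10/2300 = 4.35 (2.08 to 8.00) | none |
| 10 | 3 | 13/2300 = 5.65 (3.01 to 9.67) | 3/10 = +30% |
| 10 | 5 | 15/2300 = 6.52 (3.65 to 10.76) | 5/10 = +50% |
| 40 | 0 | 40/2300 = 17.39 (12.42 to 23.68) | none |
| 40 | 3 | 43/2300 = 18.70 (13.53 to 25.18) | 3/40 = +8% |

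**Step 4. Can the number of false cases be estimated?** Children with missed prior disease = 2300 × share of the cohort at risk × prevalence that the entry screen misses. The documents give neither input. For infants under 3 months, assume a share of 10% to 40% and a missed prevalence of 0.05% to 2%:
- low: 2300 × 0.10 × 0.0005 = 0.1
- high: 2300 × 0.40 × 0.02 = 18

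That is 0.1 to 18 infants before any case review. The range runs from negligible to dominant, so no estimate of the bias is possible.

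**The case against.** The strongest reply is that the protocol already has a control aimed at this problem. Every potential case is checked for disease before contrast, and the notes are searched for congenital forms. What remains is narrow: outside disease that left no trace in KPNC data or notes. This stands, and a reader who infers that prevalent disease simply does enter as incident goes further than sections 9.3.3 and 9.8 allow.

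Second, 3 months is a floor. All available history is used, and by inference persistent treated disease would often produce a code, a test or a prescription within 3 months of joining. This also stands, and it is why the shares in Step 1 do not measure bias.

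Third, some waiver is unavoidable, since a child under 3 months cannot have 3 months of membership. An infant enrolled from birth has complete history, and no exempt infant can have as much as 3 months unobserved. A reader might infer that the entry screen is empty for young infants in general. The text shows only that it can be empty, for those who were not members from birth.

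Section 9.4 might seem to settle the matter: "KPNC membership is stable and more than 97% of members have 5 or more years of membership". It does not, because no child under 4 can have 5 years of membership. It is a general description of the database and says nothing about lookback in this cohort.

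Finally, one might conclude that infants who joined after birth should be removed. The documents do not support that step. It could take out some of the children whom section 7 regards as most susceptible, and their number is unknown.

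**Conclusion.** The point holds as a gap in the design, not as a demonstrated bias. Exclusions without a time limit rest on 3 months of guaranteed history, or none under 3 months of age because membership from birth is not required. Prevalent disease seen only outside KPNC can pass entry and be counted as incident. The planned review narrows this but does not close it. Where prior status cannot be observed, its default works towards attributing the case to contrast.

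The effect is about 0.43 per 1000 person-years for each false case, assuming 2300 person-years. The relative effect depends on the number of true cases, and the case counts shown are assumptions. The number of false cases cannot be derived from the documents, so no claim about the total size of the bias is justified.

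**What to change.** Leave eligibility as it is and add the following to sections 9.3.3 and 9.7:

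1. Repeat all incidence rates (all cases and each category) in children who were continuous KPNC members from birth, by newborn enrolment, to exposure. Define newborn enrolment in advance, so that infants whose enrolment was recorded a few days late are handled consistently.
2. Report infants under 3 months who were not enrolled from birth as a separate stratum.
3. Report the distribution of lookback by age band.
4. At adjudication, flag cases whose thyroid status before exposure cannot be observed, instead of defaulting them to probable iodine-induced. State whether flagged cases stay in the all-cases rate.

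The cost is one repeated analysis, one table and one adjudication flag. The enrolment dates are already needed to apply the membership rule in section 9.2.3. The downside is that the from-birth subset is smaller, so its intervals are wider.

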### **9.3.2 Exposure**

Exposure will be identified through CPT codes for procedures that include iodinated contrast agent. The date the procedure was coded will be considered the date of exposure. The majority of these will be CT scans with contrast. We will also identify young children who had a left heart catheterization including cardio-angiography, ventriculography, and coronary angiography. Each child will be followed for up to 365 days after a qualifying exposure (the exposure window).

There will be no differentiation according to any specific brand of contrast agents, considering that there is general agreement that iodine induced hypothyroidism is considered a class-effect of all iodinated contrast agents and not restricted to specific agents

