### **9.3.3 Outcome measures**

Potential cases of hypothyroidism will be defined by:

- A coded diagnosis of hypothyroidism and/or
- A thyroid function tests indicating hypothyroidism and/or
- New use of thyroid replacement therapy

Cases of hypothyroid will be identified using ICD 9 DM codes, lab values and NDC codes. See appendix for code lists. From the exposed population we will identify all children who have a diagnosis of hypothyroidism in the 365 days after iodine contrast exposure. We will also identify those with lab values for low thyroid (TSH > 5.0 mU/L) or receipt of thyroid

replacement therapy in the 365 days post exposure. All children who meet any of these criteria will be considered potential cases of hypothyroidism. We will review the electronic record of each child considered to be a potential case to confirm that they did not have hypothyroidism prior to exposure to the iodine contrast agent. We will also look for codes that support the presence of the hypothyroid condition. For example if a child receives more than one prescription for thyroid replacement, or has multiple labs with high TSH levels, or multiple codes for hypothyroidism these will be considered likely cases. We will then obtain original clinical notes to validate the diagnosis, by searching for evidence of pre-existing thyroid conditions. Specifically will look for a positive diagnosis of hypothyroid, lab results, repeated lab tests, notes of other medications associated with lowered thyroid (see appendix 3 for list of drugs), and of Hashimoto thyroiditis, radiation, surgical procedures (see appendix 3 for list of procedures), and congenital forms of hypothyroid.

After review of their electronic medical record, detected cases will be classified into:

- Probable iodine-induced hypothyroidism: no other cause than the previous iodine contrast medium exposure could be identified
- Possible alternative etiology: Known other diseases (e.g. Hashimoto thyroiditis) or treatments (e.g. radiotherapy, drug treatments such as TK inhibitors, interferons, amiodarone and others) which may cause hypothyroidism
- Not a hypothyroidism case: No evidence of hypothyroidism in the patient's medical record, e.g. coding error

Estimated incidence rates will be calculated for all hypothyroidism cases together, and separate for "possible iodine induced hypothyroidism" and "possible alternative etiology."

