## **9.7 Data analysis**

Incidence density rates will be calculated using person-time of follow up. Baseline characteristics of the cases with hypothyroidism and of the rest of the cohort as well as the time-relation between iodine contrast exposure and diagnosis of hypothyroidism will be described using descriptive statistics. This will be done for all hypothyroidism cases and separately for the “probable iodine induced” category and the “possible alternative etiology” category. In the “probable iodine induced” category we will further ascertain the duration of the hypothyroidism episode.

If sample size and number of hypothyroidism cases allows, joint associations between possible risk factors and hypothyroidism will be examined in a multivariate statistical model (e.g. age, sex, bodyweight, type of procedure)

CCI

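### Requiring two weeks of membership after contrast exposure makes cohort entry depend on post-exposure status, although the planned person-time analysis already handles short follow-up

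*Combined protocol and SAP*

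**What the plan says.** Section 9.2.3 (Study population) asks for three months or more of KPNC membership ahead of the contrast procedure, "except where the child is under 3 months of age at time of initial exposure, and 2 weeks after the exposure". The age exception relaxes the look-back before exposure. On the natural reading, the two weeks after exposure apply to every child.

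The other relevant sections start the clock at exposure:

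- Section 9.3.2: "The date the procedure was coded will be considered the date of exposure". Follow-up then lasts for up to 365 days, so shorter follow-up is allowed.
- Section 9.3.3: "we will identify all children who have a diagnosis of hypothyroidism in the 365 days after iodine contrast exposure". The first 14 days are not carved out.
- Section 9.7: "Incidence density rates will be calculated using person-time of follow up".

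The protocol gives no reason for the two-week condition. It states no rule for ending person-time at death or disenrolment, and it plans no count of the children whom the condition removes. Section 9.9 (Limitations) does not mention it, and the Annex 2 checklist marks selection bias as not applicable (item 12.1.1).

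**The concern.** Whether a child enters at day 0 is decided by something observed at day 14. Suppose hypothyroidism is detected on day 6 and membership ends on day 12. That child disappears from the numerator and the denominator, although section 9.3.3 would otherwise count the case.

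The primary objective (section 8.1) is the rate in exposed children over the 365 days after exposure. The condition changes this to exposed children still enrolled two weeks later, and the protocol does not say so.

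The early period matters on the protocol's own account. Section 7 states: "Excessive free iodide may inhibit thyroid hormone synthesis, causing hypothyroidism through an acute Wolff-Chaikoff effect". It describes neonates as especially susceptible. The cohort includes infants under 3 months and children undergoing left heart catheterization, among whom early deaths are plausible. A secondary objective is the time relation between exposure and diagnosis, and selection on the first 14 days could distort the early part of that distribution.

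**Working it through.** **No plan figure to reproduce.** The only size given is a count: "A preliminary search of the data identified around 2300 people under age 4 who had a procedure with iodinated contrast" (section 9.2.3). It precedes the membership and thyroid exclusions. The documents give no expected rate, mortality or disenrolment figure.

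**Inputs**

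- N = 2300 (sections 9.2.3 and 9.5).
- d, the share leaving or dying by day 14: assumed 1% or 2%, with mean exit at day 7.
- r, the one-year risk in retained children: assumed 1%, with events at mid-year on average.
- q, the risk of a detected case before exit in those removed: varied. The highest value used is 8.3%, the figure for term infants in section 7.

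**Formulas** (year of 365.25 days)

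- Removed children = N × d; their person-years = N × d × 7/365.25.
- Retained cases = N(1−d) × r.
- Retained person-years = N(1−d) × (1 − r/2) × 365/365.25.
- Restricted rate = retained cases / retained person-years.
- Full-cohort rate = (retained cases + N × d × q) / (retained + removed person-years).

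**Numbers for d = 1%**

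- Removed: 23 children, 23 × 7/365.25 = 0.44 person-years.
- Retained: 2277 children, 22.77 cases, 2277 × 0.995 × 365/365.25 = 2264.06 person-years.
- Restricted rate: 22.77/2264.06 = 10.06 per 1000 person-years.
- With q = 8.3%: 23 × 0.083 = 1.91 cases lost. Full-cohort rate (22.77 + 1.91)/2264.50 = 10.90. The restricted rate is 1 − 10.06/10.90 = 7.7% too low.

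**Numbers for d = 2%**

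- Removed: 46 children, 0.88 person-years.
- Retained: 2254 children, 22.54 cases, 2241.19 person-years; restricted rate again 10.06.
- With q = 8.3%: 46 × 0.083 = 3.82 cases lost. Full-cohort rate (22.54 + 3.82)/2242.07 = 11.76. The restricted rate is 14.5% too low.

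**Understatement of the restricted rate, by scenario**

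| Risk before exit in removed children | d = 1% | d = 2% |
|---|---|---|
| Same constant hazard as retained (q ≈ 0.01 × 7/365 = 0.0002) | 0.0% | 0.0% |
| Same 1% risk, all before exit | 1.0% (0.23 cases lost) | 2.0% (0.46 cases lost) |
| 8.3%, all before exit | 7.7% (1.91 cases lost) | 14.5% (3.82 cases lost) |

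These percentages depend on d, r and q but not on N, so the pre-exclusion base of 2300 does not affect them. It does affect the counts. Removing early leavers takes almost nothing from the denominator, so any effect comes from the cases removed with them.

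**The case against.** **Size.** The 8.3% comes from neonatal studies that section 7 itself describes as strongly affected by bias. Applying it to every early leaver under age 4, with all cases detected before exit, is extreme. For d = 1% it implies 1.91 cases in 0.44 person-years, about 4,300 per 1000 person-years and some 430 times the 10.06 in retained children. Section 9.4 calls membership stable, with over 97% of members having at least five years, so voluntary exit within two weeks should be rare. Section 9.3.2 expects most exposures to be CT scans, so catheterization patients are a minority. This all stands, and the 8.3% row is an upper-end value only.

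**A possible purpose.** The target is hypothyroidism detected in routine practice, and support for a case draws on repeat tests, codes or prescriptions. A child observed for a few days offers little chance of either. That is a reasonable argument for a minimum observation period, but the protocol does not make it. A sensitivity analysis would serve it without redefining the primary cohort.

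**Censoring.** Ending person-time at death is not neutral in very sick children, because death may be informative. This stands, and is why deaths should be reported as a competing event.

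**Stronger readings that a reader might infer.** Three are not supported:

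- That all early cases in high-risk children are lost. Cases on days 1-14 in retained children count under section 9.3.3; only those in children who also exit by day 14 are lost.
- That this is immortal time bias. Retained children can have the outcome, and be counted, during those 14 days.
- That 2-10 cases are lost (2300 × 1-5% × 8.3% = 1.9-9.5). The documents support neither the exit share nor the use of 8.3% for all leavers.

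The documents also do not say that death ends membership, or how many days the acute effect lasts.

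**Conclusion.** The structural point holds on the text. Entry is conditioned on a post-exposure status, counting begins at exposure, and the planned measure does not need the condition. Nothing elsewhere in the protocol acknowledges or offsets it.

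Its size is unknown. At an assumed 1-2% early exit and 1% one-year risk in retained children, the rate runs from essentially unchanged, through about 1-2% too low, to 7.7-14.5% too low at the upper-end 8.3%. For scale, the relative standard error of a Poisson count of 22.77 is 1/√22.77 = 21%, so even the upper-end effect is smaller than one standard error under these assumptions. Deaths matter more than voluntary exits, on the inference that death ends membership. Confidence is high in the selection and low in its magnitude. The change is worth making because it is cheap and because, as planned, a reader of the report could not judge the effect.

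**What to change.** - In section 9.2.3, delete the requirement of two weeks' membership after exposure from the primary cohort definition.
- In section 9.7, state that person-time starts at the index exposure and ends at the first of hypothyroidism, death, disenrolment, day 365 or end of data.
- Report the numbers of deaths (as a competing event) and disenrolments by day 14 and by day 365.
- Keep the 14-day restriction as a sensitivity analysis, with its reason stated.

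The cost is a few edited sentences and one extra tabulation and analysis. The study uses secondary data only, so no new data collection is needed. The small downside is that a few children with very short follow-up, and little chance of detection or validation, enter the cohort. They add negligible person-time: 0.44-0.88 person-years at 1-2% early exit.
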